1.1 Study rationale

This Statistical Analysis Plan (SAP) explains in detail the statistical analyses that will be carried out for Pharmamar in PM104 – B – 001 – 09 study. The analyses described in this SAP are based upon and supplement those described in the study protocol (dated 27-Jan-2009).

1.2 Information on Study Drug

PM00104 is a new synthetic alkaloid that has been selected for clinical development based on its in vitro activity against human solid and non-solid tumor cell lines, its in vivo activity in xenografted human tumors, as well as an acceptable non-clinical toxicology profile.

2 Objectives

The study protocol states the following:

2.1 Primary

- To evaluate the antitumor activity of PM00104 administered as a 1-hour intravenous (i.v) infusion on Day 1, 8 and 15 every four weeks (d1, d8 and d15; q4wk) to patients with advanced and/or metastatic endometrial or cervical cancer previously treated with one line of systemic chemotherapy.

2.2 Secondary

- To determine the safety profile of this PM00104 regimen in these patients.
- To determine the pharmacokinetic (PK) profile of this PM00104 regimen in these patients.
- To determine the pharmacogenomic (PGx) profile of this PM00104 regimen in these patients. Hypothesis-generating exploratory PGx analyses will be conducted to correlate the molecular parameters found in the tumor samples of the patients with the clinical results achieved with PM00104.

3 Study design

Multicenter, open label, phase II clinical trial with single-agent PM00104 given as a 1-hour i.v. infusion on d1, d8 and d15 q4wk to patients with advanced and/or metastatic endometrial or cervical cancer progressing after at least one line of systemic chemotherapy.

The primary endpoint of the study is the overall response rate (ORR), defined as the percentage of patients with objective response (OR; complete or partial response) as defined by the Response Evaluation Criteria in Solid Tumors (RECIST).

4 Study populations

4.1 Analysis populations

Female adult patients with endometrial (Group 1) or cervical cancer (Group 2) progressing after at least one previous line of systemic chemotherapy are eligible for this trial. To be included in the study, patients have to fulfill all inclusion criteria and none of the exclusion criteria.

4.1.1 Efficacy population

To be evaluable for efficacy, patients must have received at least four infusions of the six infusions in the first two cycles and at least one disease measurement recorded not less than six weeks after treatment onset will be evaluable for efficacy.

In addition, any eligible patient who receives at least two of the three infusions in one treatment cycle and experience disease progression or die due to progressive disease (PD) prior to response evaluation will be considered evaluable for the main endpoint (ORR) and will be categorized as an “early progression”.

Patients withdrawn due to toxicity without any tumor assessment after the start of study treatment will be considered as “treatment failures” and will not be replaced.

Patients withdrawn due to significant clinical deterioration of unknown reason, hypersensitivity reactions, refusal to continue on study for any reason or unrelated AEs without any tumor assessment after the start of study treatment will be considered not evaluable for efficacy and will be replaced.

4.1.2 Safety population

All patients who have received at least one complete or partial infusion of PM00104 infusion will be included in the safety analysis.

5 Endpoints

5.1 Primary endpoints

Overall response rate (ORR), defined as the percentage of patients with confirmed objective response (OR), either complete (CR) or partial (PR) response according to the RECIST.

5.2 Secondary endpoints

- Progression-free survival at four months (PFS4 rate), defined as the percentage of patients who are alive and with no evidence of disease progression at four months after the first study drug administration.
- Progression-free survival rate at six months (PFS6), defined as the percentage of patients who are alive and with no evidence of disease progression at six months after the first study drug administration.
- Duration of response (DR), defined as the time between the date when the response criteria (PR or CR, the first that is reached) are fulfilled and the first date when disease progression, recurrence or death is objectively documented (taking the smallest measurements documented since the treatment started as reference for progressive disease).

- Progression-free survival (PFS), defined as the time from the first day of study treatment to the day of negative assessment (progression or death) or last tumour evaluation.
- Overall survival (OS), defined as the time from the first day of treatment to the date of death (or the last day when the patient is known to be alive). Survival will be followed for up to six months after the treatment discontinuation of the last patient.
- Safety profile: AEs, SAEs, laboratory evaluations, deaths and the reason for study discontinuations, dose delays, modifications or omissions will be analyzed. All AEs and SAEs will be classified according to the NCI-CTCAE, version 3.0, and will be coded using the Medical Dictionary for Regulatory Activities (MedDRA), version 10.0.
- Treatment exposure:
 - *Date of treatment start*: Date of treatment dose at cycle 1.
 - *Date of last dose*: Date of last treatment dose at last cycle.
 - *Date of treatment discontinuation (for the purpose of exposure calculations)*: The minimum date between the death date and the date of the first infusion of last cycle + 28 days.
 - *Body Surface Area (BSA)*: The calculated surface of a human body measured in m².
 - *Treatment duration*: The time between the day of the first dose and the day of treatment discontinuation (in weeks).
 - *Total cumulative dose*: The sum of all the PM00104 doses from the first cycle until last cycle including the dose received in last cycle. (Expressed in mg/m²).
 - *Absolute dose intensity*: The actual cumulative dose divided by number of weeks of treatment. (Expressed in mg/m²/wk).
 - *Intended dose intensity*: The planned dose per cycle divided by the planned weeks by cycle. (Expressed in mg/m²/wk).
 - *Relative dose intensity*: The ratio of absolute dose intensity (x100) divided by the intended dose intensity. (Expressed in percentage).
- Pharmacokinetic/Pharmacodynamic parameters.
- Pharmacogenomic profile

6 Sample size

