7.2. ADMINISTRATION OF STUDY MEDICATION

7.2.1. Dose Schedule

A treatment cycle consists of the administration of three i.v. 1-hour infusions of PM00104 on Day 1, Day 8 and Day 15, and all study evaluations done before the next cycle. Treatment cycles will be repeated every four weeks.

The starting dose in each infusion is 2 mg/m². This is the recommended dose for phase II studies found in the phase I study PM104-A-004-05 (see Section [1.3.5](#)).

The study treatment will be administered to the patients by a central catheter and by specialized on-site study personnel. Central catheter is mandatory as some cases of infusion site reactions were observed in the phase I trials (see Section [1.3.5.4](#)).

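### SAP 5.2 stops the exposure clock at death but compares against an intensity averaged over the full 28-day cycle, so a Cycle 1 death before the Day 15 dose, with no dose skipped, yields a relative dose intensity of at least 133%

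*SAP*

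**What the plan says.** SAP section 5.2, under treatment exposure, builds RDI in a chain:

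- The end of exposure is "The minimum date between the death date and the date of the first infusion of last cycle + 28 days". The SAP labels this date as being for exposure calculations.
- Treatment duration is the elapsed time, in weeks, from the first dose to that end date.
- Cumulative dose is "The sum of all the PM00104 doses from the first cycle until last cycle including the dose received in last cycle".
- Absolute dose intensity is "The actual cumulative dose divided by number of weeks of treatment".
- Intended dose intensity is "The planned dose per cycle divided by the planned weeks by cycle".
- RDI is "The ratio of absolute dose intensity (x100) divided by the intended dose intensity".

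The schedule is in Protocol 7.2.1: "A treatment cycle consists of the administration of three i.v. 1-hour infusions of PM00104 on Day 1, Day 8 and Day 15", repeated every four weeks, and "The starting dose in each infusion is 2 mg/m²". No dose is therefore due after Day 15 of a cycle.

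SAP Table 12.1.1.3 reports cumulative dose, treatment duration, dose intensity and RDI by N, median, minimum and maximum, separately for each tumor group. Neither document caps RDI, adjusts the intended intensity when death cuts the last cycle, or covers a duration of zero.

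**The concern.** A patient who stops treatment alive has her last cycle counted as 28 days, which matches the basis of the intended intensity. A patient who dies has that cycle cut to the days she lived, while the intended intensity stays at its 28-day average. All doses fall in the first 15 days of the cycle, so the cut removes mostly dose-free time and raises the computed rate. The ratio then has its numerator on one time basis and its denominator on another.

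The consequence is a misleading exposure table. A patient who received a third or two thirds of a planned cycle can appear to have received well over the planned intensity, purely because she died. With about 30 patients per group, one such case can set the reported maximum.

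**Working it through.** **Inputs.** 2 mg/m² per infusion, Days 1, 8 and 15, 4-week cycle (Protocol 7.2.1); the exposure definitions in SAP 5.2. Durations are elapsed days, as the SAP defines them: first dose on Day 1 and death on Day 10 is 9 days.

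**The plan's own figure.** Intended intensity = 3 × 2 / 4 = 1.5 mg/m²/week. This reproduces the value in Protocol Table 6 and section 1.4.

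**Formula.** With *c* earlier cycles given in full and on time, *D* full doses in the last cycle, and death *t* days (*t* ≤ 28) after that cycle's Day 1:

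RDI = 100 × [(6c + 2D) / ((28c + t)/7)] / 1.5

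**Same dosing, different vital status (c = 0, D = 2).**
- Alive at 28 days: 4 / 4 = 1.00 mg/m²/week; 1.00 / 1.5 = 67%.
- Died on Day 10 (t = 9): 4 / (9/7) = 3.11 mg/m²/week; 3.11 / 1.5 = 207%.

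**Death in Cycle 1 before the Day 15 dose, nothing skipped.**

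| Doses | Days from first dose to death | RDI under SAP rule | RDI with last cycle = 28 days |
|---|---|---|---|
| 1 | 1 | 933% | 33% |
| 1 | 4 | 233% | 33% |
| 1 | 7 | 133% | 33% |
| 2 | 8 | 233% | 67% |
| 2 | 9 | 207% | 67% |
| 2 | 14 | 133% | 67% |

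The lowest value is 133%: 2 / (7/7) / 1.5, or equally 4 / (14/7) / 1.5. At t = 0 the divisor is zero and RDI is undefined.

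**Later cycles, death before the Day 15 dose, earlier cycles full and on time.**
- Cycle 2: 106.7% (8 / 5 / 1.5) to 129.6% (10 / (36/7) / 1.5).
- Cycle 3: 103.7% to 116.7%.
- Cycle 4: 102.6% to 111.6% (maximum 22 / (92/7) / 1.5).
- Cycle 6: 101.6% to 107.2%.

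**Where the effect disappears.** In Cycle 1, RDI exceeds 100% only if t < 9.33 days with one dose or t < 18.67 days with two. After a skipped infusion, one dose with death at 13 days gives 71.8%, and two doses with death at 20 days give 93.3%.

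**All three doses given.** Cycle 1 deaths at 15 to 27 days give 187% down to 104%. That is inflation too, but no planned dose of that cycle was missed.

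**How likely such a case is.** The documents give no early-death rate. If 1% to 5% of patients died before their first Day 15 dose (an assumption), the chance of at least one among 30 would be 1 − 0.99³⁰ = 26% to 1 − 0.95³⁰ = 79%.

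**The case against.** **It is one convention among several.** A patient who dies on Day 10 after both due doses missed nothing while alive, so scoring her 67% charges her for an infusion she could not receive. Comparing dose received with dose due up to death would give 4/4 = 100%. It is true that 67% is not the only defensible answer. But both consistent bases give 67% or 100%; the SAP rule gives 207% because it mixes them.

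**Such deaths should be few.** Protocol 4.1 requires a life expectancy of at least 3 months and ECOG status of 1 or less. That limits frequency, and the median would move little. However, the safety population takes anyone with even a partial infusion (SAP 4.1.2), and SAP 4.1.1 provides for deaths from progression before response evaluation.

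**Other columns would reveal it.** Cumulative dose and duration sit in the same table. They are summarized separately, though, and SAP 12.1.1 has no patient listing that ties a high RDI to a low cumulative dose.

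**Stronger readings that the documents do not support.** A reader might infer that every death in the last cycle gives an RDI far above 100%; the later-cycle and skipped-dose results rule that out. A reader might expect a distorted mean; the table shell has no mean column, although the general rule in Protocol 10.3 lists one. A reader might fear a spurious link between exposure and death; SAP 7.3 only describes exposure, and no exposure–survival analysis is specified. Nor is the SAP's end date in error merely because the Protocol dates discontinuation at the last dose: the SAP restricts its date to exposure calculations.

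**Conclusion.** The point stands as a minor defect in a definition. In Cycle 1 deaths before the Day 15 dose, with full doses on schedule and none skipped, the SAP rule gives an RDI of 133% or more, or no value at all if death falls on the day of the first dose. Earlier delays, skips or reductions lower the later-cycle figures, which assume full, on-time dosing beforehand. The practical damage is mainly to the maximum in Table 12.1.1.3, and how often it occurs cannot be judged from the documents. The overall response rate and the two-stage decision rules do not use RDI and are not affected.

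**What to change.** In SAP 5.2, separate the two uses of the end date:

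- For absolute and relative dose intensity only, run the weeks of treatment from the first dose to 28 days after Day 1 of the last cycle, for every patient whether or not she died.
- For reported treatment duration, keep the existing date truncated at death, so that duration does not run past death.
- In Table 12.1.1.3, footnote the patients who died within the last cycle, because for them cumulative dose divided by reported duration will no longer equal the tabulated intensity.

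This also removes the zero-duration case. It changes an analysis definition only and needs no new data.

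The cost is that a patient who dies mid-cycle is scored against doses she could not live to receive, so her RDI falls substantially: 207% becomes 67% in the example. The footnote lets a reader see why.

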6.1 Sample size determination

In this phase II trial, efficacy of PM00104 will be evaluated in two different groups of patients with endometrial or cervical cancer.

Group 1 (endometrial cancer): A Simon two-stage design will be adopted in this group to test the null hypothesis that the ORR by RECIST is $\leq 10\%$ versus the alternative that ORR $\geq 30\%$ (two-sided test; $\alpha=0.1$ and $\beta=0.1$).

A maximum of 30 evaluable patients will be included in this group. In a first stage, 10 evaluable patients will be recruited. If one or more (≥ 1) patients achieve an objective response, the accrual in this group will be expanded with 20 additional evaluable patients.

If the total number of patients with objective response is 6 or more (≥ 6) in 30 evaluable patients (i.e., an ORR in the whole study of at least 20%), the null hypothesis will be rejected and PM00104 will be considered for further clinical development in endometrial cancer.

Group 2 (cervical cancer): Also a Simon two-stage design where the null hypothesis ORR by RECIST is $\leq 5\%$ vs. ORR $\geq 20\%$ (two-sided test; $\alpha=0.1$ and $\beta=0.1$).

A maximum of 32 evaluable patients will be included in this group. In a first stage, 18 evaluable patients will be recruited. If one or more (≥ 1) patients achieve an objective response, the accrual in this group will be expanded with 14 additional evaluable patients.

If the total number of patients with objective response is 4 or more (≥ 4) in 32 evaluable patients (i.e., an ORR in the whole study of at least 12.5%), the null hypothesis will be rejected and PM00104 will be considered for further clinical development in cervical cancer.

6.2 Interim analyses

Interim efficacy analysis will be performed when the 10 first evaluable patients have been recruited in the group 1 and 18 patients have been recruited in the group 2. In addition, a safety evaluation will be performed when 10 patients in each group will be recruited and followed for at least four weeks. The study will be stopped, and the recommended dose re-evaluated if the stopping rule described below is met in any of the groups.

Other non-scheduled interim analyses might be performed exclusively for enhancing the safety of the patients.

Early stopping rule:

An early stopping rule for excessive toxicity will be evaluated when ten patients in each group will be recruited and followed for at least four weeks. A "serious toxicity" rate (STR) of 40% or more will be considered inadequate. The following are considered serious toxicities:

- Drug-related grade 4 neutropenia lasting for more than seven days.
- Grade 4 thrombocytopenia.
- Grade 3/4 nausea/vomiting despite adequate prophylaxis.
- Grade 3/4 transaminase increase lasting for more than seven days.
- Grade 3/4 fatigue.
- Any other grade 3/4 drug-related event leading to early study discontinuation.

If ≥ 4 patients of the first 10 patients had one of these serious toxicities, the trial will be stopped and the recommended dose and/or administration schedule for phase II will be re-evaluated.

With this stopping rule, the probability of $\geq 4/10$ STR in the sample (if the true probability of STR is $< 1/6$) is 0.0697. On the other hand, the probability of observing $\leq 3/10$ STR in the sample (if the true probability of STR is $> 40\%$) would be 0.3822.

7 Statistical analysis

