A Simon two-stage design will be adopted in this group to test the null hypothesis that the ORR by RECIST is $\leq 5\%$ *versus* the alternative that $\text{ORR} \geq 20\%$ (two-sided test; $\alpha=0.1$ and $\beta=0.1$). A maximum of 32 evaluable patients will be included in this group. In a first stage, 18 evaluable patients will be recruited. If one or more (≥ 1) patients achieve an objective response, the accrual in this group will be expanded with 14 additional evaluable patients. If the total number of patients with objective response is 4 or more (≥ 4) in 32 evaluable patients (i.e., an ORR in the whole study of at least 12.5%), the null hypothesis will be rejected and PM00104 will be considered for further clinical development in cervical cancer.

Early stopping rule

An early stopping rule for excessive toxicity will be evaluated when ten patients in each group will be recruited and followed for at least four weeks. A "serious toxicity" rate (STR) of 40% or more will be considered inadequate. The following are considered serious toxicities:

- Drug-related grade 4 neutropenia lasting for more than seven days.
- Grade 4 thrombocytopenia.
- Grade 3/4 nausea/vomiting despite adequate prophylaxis.
- Grade 3/4 transaminase increase lasting for more than seven days.
- Grade 3/4 fatigue.
- Any other grade 3/4 drug-related event leading to early study discontinuation.

If ≥ 4 patients of the first 10 patients had one of these serious toxicities, the trial will be stopped and the recommended dose and/or administration schedule for phase II will be re-evaluated.

With this stopping rule, the probability of $\geq 4/10$ STR in the sample (if the true probability of STR is $< 1/6$) is 0.0697. On the other hand, the probability of observing $\leq 3/10$ STR in the sample (if the true probability of STR is $> 40\%$) would be 0.3822.

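### The 4-of-10 serious-toxicity rule is read once, after ten patients have four weeks of follow-up, although the fourth event already fixes the decision to stop

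*SAP*

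**What the plan says.** Protocol 10.1 (Early stopping rule) and SAP 6.2 give the same rule. A serious-toxicity "rate (STR) of 40% or more will be considered inadequate". The rule "will be evaluated when ten patients in each group will be recruited and followed for at least four weeks", and the boundary is a count: "If ≥ 4 patients of the first 10 patients had one of these serious toxicities, the trial will be stopped".

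SAP 6.2 adds that the study stops "if the stopping rule described below is met in any of the groups", so a crossing in one tumour group ends both. SAP Table 12.2.2.1 uses the first ten consecutive patients per group as the denominator.

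Both documents give two operating characteristics. The probability of stopping is 0.0697 at a true rate of 1/6. The probability of not stopping is 0.3822 at 40%.

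SAP 6.2 also permits unscheduled interim analyses for patient safety. It gives them no trigger, schedule or boundary, and Protocol 10.1 does not mention them.

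**The concern.** The boundary is a cumulative count of affected patients. If four of the first seven have a listed toxicity, the result for the first ten must be at least four, whatever happens to patients eight, nine and ten. The plan nevertheless sets one reading, after the tenth patient's four weeks. It does not say that the rule takes effect at the fourth event, and it does not pause entry before the reading.

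Patients could therefore start a regimen that the trial's own rule is already bound to send back for re-evaluation. Because either group can stop the study, patients entering the other group are exposed meanwhile too. The phrase "a safety evaluation will be performed when 10 patients in each group will be recruited and followed for at least four weeks" can also be read as waiting for both groups to reach ten, which would lengthen the delay.

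**Working it through.** **1. The plan's own figures.** Let X be the number affected among ten patients, X ~ Bin(10, p).

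- At p = 1/6: P(X ≥ 4) = 1 − (0.1615 + 0.3230 + 0.2907 + 0.1550) ≈ 0.0697, as stated.
- At p = 0.40: P(X ≤ 3) = 0.0060 + 0.0403 + 0.1209 + 0.2150 = 0.38228. This is printed as 0.3822 and rounds to 0.3823.

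**2. Same boundary, applied when it is reached.** Let K be the entry number of the patient with the fourth event:

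P(K = k) = C(k−1, 3) p⁴ (1−p)^(k−4), for k = 4 to 10.

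At p = 0.40 the terms are 0.0256, 0.0614, 0.0922, 0.1106, 0.1161, 0.1115 and 0.1003, which sum to 0.6177. This equals 1 − 0.3823. The equality is exact for every p, because the count is at least 4 at the end if and only if it reached 4 on the way. Acting at the fourth event leaves both stated probabilities unchanged.

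**3. Upper bound on later entries.** This assumes that each outcome is known before the next patient enters.

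| True rate | P(stop) | Mean K given stop | Entries after K, given stop | K before patient 10, given stop |
|---|---|---|---|---|
| 1/6 | 0.0697 | 8.4 | 1.6 | 69% |
| 40% | 0.6177 | 7.6 | 2.4 | 84% |
| 50% | 0.8281 | 7.0 | 3.0 | 90% |
| 60% | 0.9452 | 6.4 | 3.6 | 95% |

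These averages are conditional on a stop. Unconditionally, at 40%, the figure is 0.6177 × 2.44 = 1.5 patients per group.

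**4. Allowing for delay.** The documents give 30 and 32 evaluable patients (Protocol 10.1) and 24 months of enrolment (Protocol 5.1). These give 30/24 = 1.25 and 32/24 = 1.33 patients per month. The remaining inputs are assumptions: a constant rate with random (Poisson) arrivals, toxicity onset uniform over 28 days, and either 0 or 14 further days before the event is recognised. The evaluation is placed 28 days after the tenth entry. Simulated results given a stop:

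| True rate | Recognition lag | First-ten patients entering after the fourth event is known (1.25 / 1.33 per month) | Months from then to the evaluation (1.25 / 1.33 per month) |
|---|---|---|---|
| 40% | 0 days | 1.98 / 1.95 | 2.4 / 2.3 |
| 40% | 14 days | 1.59 / 1.55 | 1.9 / 1.8 |
| 50% | 0 days | 2.50 / 2.47 | 2.8 / 2.7 |
| 50% | 14 days | 2.05 / 2.00 | 2.4 / 2.2 |
| 60% | 0 days | 3.12 / 3.08 | 3.4 / 3.2 |
| 60% | 14 days | 2.61 / 2.55 | 2.9 / 2.7 |

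**5. Entry during the final four weeks.** If entry is not paused, a further 1.25 × 28/30.44 = 1.15 to 1.33 × 28/30.44 = 1.23 patients per group would enter. In Group 1 the stage-one efficacy look also falls at ten evaluable patients and might hold entry. In Group 2 it falls at 18, so it would not.

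**The case against.** The strongest reply is that the plan dates a scheduled evaluation and nowhere forbids earlier action. A reader might infer that sites are obliged to enrol to patient ten regardless. The documents do not say that; they are silent. There are real safeguards:

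- Serious adverse events reach the sponsor within 24 hours (Protocol 9.2.2).
- The sponsor confirms each registration (Protocol 5.6).
- Unscheduled safety analyses are allowed (SAP 6.2).
- Protocol 11.1 adopts the Declaration of Helsinki, whose paragraph 20 requires immediate stopping when risks are found to outweigh benefits.

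All of this stands. None of it sets a trigger at the fourth event, however, and not every listed toxicity need be a serious adverse event.

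A reader might also infer that everyone on treatment continues unchanged. That is too broad. Protocol 5.2.1.2 and 7.2.3 provide discontinuation and dose reduction for affected patients. Those rules do not stop new entries.

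Nor are the later patients uninformative. They contribute pharmacokinetic, safety and response data, and may inform the re-evaluation of dose and schedule. Only the stop decision is beyond their influence.

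Finally, some listed toxicities must last more than seven days and one must lead to early discontinuation, so recognition takes time. This is why 2.4 to 3.6 is an upper bound. It shortens the gap without closing it.

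**Conclusion.** The point holds as one of timing. The rule is the same in both documents, and its stated probabilities are right apart from the last digit of 0.3822. What is missing is a statement that the boundary operates when it is reached.

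Given a stop at true rates of 40% to 60%, about 1.6 to 3.1 of the first ten patients in a group would enter after the fourth event is known. The scheduled evaluation would follow about 1.8 to 3.4 months later. These figures rest on the accrual, onset and recognition assumptions shown above. The ceiling, with immediate knowledge of each outcome, is 2.4 to 3.6 patients. The documents do not support a claim that the plan compels this exposure, or that the error rates are wrong. They do leave it to discretion, and a pre-specified safety boundary should not depend on that. The change is worth making.

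**What to change.** In Protocol 10.1 and SAP 6.2, add a sentence to this effect:

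> The boundary is met, and new accrual is halted in both groups, as soon as a fourth patient among the first ten in either group has a confirmed listed toxicity. Otherwise it is assessed for each group when that group's tenth patient has completed four weeks.

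Halting both groups follows from the SAP's existing provision that a crossing in either group stops the study. The same sentence settles whether one group waits for the other. Keep the threshold of four, the toxicity list and the stated probabilities, and note that they are unaffected.

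The sponsor should also state what happens to patients already on treatment between the fourth event and the re-evaluation. The documents do not address this, and no clinical rule is proposed here.

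The cost is one sentence in each document and a running count per group. The count draws on data already collected: adverse event reports and the weekly laboratory tests in Protocol 5.7. Sample size and error rates do not change.
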